#### **10.7. Physical Examination**

Physical examination data (Normal/Abnormal) at each visit will be listed by body system for all randomized subjects.

#### **10.8. Columbia-Suicide Severity Rating Scale (C-SSRS)**

Two versions of the C-SSRS are to be used in the study: The first is to be used at Screening and will assess lifetime suicidal ideation and behavior until that point (Baseline-Screening Form). Identification of active suicidal ideation will exclude the subject from enrollment in the study. At each subsequent visit, the follow-up C-SSRS is used (Since Last Visit form) to assess suicidal ideation and behavior since the last visit.

The C-SSRS data, i.e. suicidal ideation severity, suicidal ideation intensity, suicidal behavior, non-suicidal self-injuries behavior and lethality, will be summarized by treatment arm and visit for the Safety Population. Additionally, a frequency table of subjects answering Yes to questions of C-SSRS form by any question will be provided by treatment arm for the Safety Analysis Set. A listing of all randomized subjects will be provided.

1

For more information, contact the Office of the Vice President for Research and Economic Development at [contact] or [[contact]](mailto:[contact]).

1

A horizontal bar composed of four thick black lines of varying lengths, with the rightmost line being the longest.

1

\_\_\_\_\_

\_\_\_\_\_

\_\_\_\_\_

\_\_\_\_\_

—

© 2019 Pearson Education, Inc.

10 of 10 pages

For more information, contact the Office of the Vice President for Research and Economic Development at [contact] or [[contact]](mailto:[contact]).

1

A series of horizontal black bars of varying lengths, with the longest bar at the bottom.

1

—  
—  
—

—  
—

\_\_\_\_\_

Digitized by [contact]

This document is confidential.

■

[REDACTED]

[REDACTED]

[REDACTED]

[REDACTED]

[REDACTED]

[REDACTED]

[REDACTED]

[REDACTED]

## 11.2. Brief Description of CHW

The Cui, Hung, Wang ([CHW; Cui, Hung et al. 1999](#)) weighted test statistic to analyze the primary and secondary efficacy endpoint (i.e., for total ESS and mean MWT) at the end of the study is described below and it preserves the type 1 error in case of updated sample size:

Cui-Hung-Wang (CHW) approach defines a weighted statistic (Z), data from the 2-stages (stage 1 uses all data until interim analysis, stage 2 uses all data after interim analysis) by weighting the stage wise Wald test statistics

Wald Test Statistic under  $H_0: \delta = 0$ , is defined as

$$\text{Stage 1: } Z_1 = (\widehat{\delta}_1 - \delta) / SE(\widehat{\delta}_1)$$

$$\text{Stage 2: } Z_2 = (\widehat{\delta}_2 - \delta) / SE(\widehat{\delta}_2)$$

Where  $\widehat{\delta}_1$  is difference in sample means at stage 1. Similarly,  $\widehat{\delta}_2$  is the difference in sample means at stage 2.  $SE(\widehat{\delta}_1)$  is standard error for  $\widehat{\delta}_1$  at stage 1. Similarly,  $SE(\widehat{\delta}_2)$  is standard error for  $\widehat{\delta}_2$  at stage 2.

The CHW pooled test statistic combines the two stages statistics together and applies the weighting,

$$Z = \sqrt{W_1} Z_1 + \sqrt{1 - W_1} Z_2$$

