## 14 STATISTICAL ANALYSIS

A SAP will be prepared after the protocol is approved. This document will provide further details regarding the definition of analysis variables and analysis methodology to address all study objectives. The SAP will serve as a complement to the protocol and supersedes it in case of differences.

The statistical evaluation will be performed using SAS® software version 9.4 or higher (SAS Institute, Cary, NC). All data will be listed, and summary tables will be provided.

Summary statistics will be presented by treatment group. For continuous variables, data will be summarized with the number of patients (n), mean, SD, standard error of mean, median, minimum, and maximum by treatment group. For categorical variables, data will be tabulated with the number and proportion of patients for each category by treatment group.

An unblinded interim analysis is planned when approximately 50% of patients have completed 14 days of treatment (Visit 3 completed). This interim analysis is for the purpose of sample size re-estimation, and futility will not be examined. Interim analysis will occur under the supervision of an independently charted DMC. See [Section 7.1.4](#).

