#### **14.3.2 Analysis of Secondary Efficacy Endpoints**

The secondary efficacy endpoints for this study are:

- Change from baseline in the mean CGI-S score related to EDS at Day 14
- Change from baseline in the mean MWT score at Day 14

To control the Type I error rate, the testing of secondary endpoints will be controlled using hierarchical testing methods. Thus, only if the primary endpoint is statistically significant, will the first listed secondary endpoint be tested. Likewise, the second listed secondary endpoint will only be tested if the first secondary endpoint is also statistically significant.

The secondary endpoints will be analyzed analogous to the analysis of the primary efficacy endpoint, i.e., an MMRM using the ITT population with the same factors, except the baseline value for the respective variable will be used instead of baseline total ESS score.

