### **14.6    Interim Analysis**

Because of uncertainty in the underlying assumption supporting the power calculation, an unblinded interim analysis is planned when approximately 50% of patients have completed 14 days of treatment (Visit 3 completed) in order to increase the sample size if this deemed necessary and thus to increase the likelihood for a positive study.

The unblinded interim analysis is for the purpose of sample size re-estimation, and futility will not be examined. Sample size re-estimation will be performed using conditional power calculations. In case of sample size increase the weighted Cui, Hung, Wang test-statistic will be used for the combination of the data prior to the interim analysis and after interim analysis.

The sample size re-estimation will permit a maximum of 57 additional patients (19 per treatment arm) to be randomized, and it will not permit a reduction in the initial sample size of 114 total patients.

Unblinded interim analysis will be performed in a firewall-protected project folder by an independent unblinded DMC statistician. Unblinded results will remain confidential. Access to unblinded interim results and documentation will be limited to the DMC and unblinded DMC statistician.

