### **3.6. Determination of Sample Size**

Sample size for the MWT which was the primary efficacy in the study until the change in primary efficacy endpoint (refer to section 2.3): This study plans to randomize 114 subjects, using 1:1:1 treatment allocation (stratified by atleast 30% each by reported cataplexy subject history, Na-1 or Na-2 respectively), 38 to each treatment group. Using an SD of 5.0, N = 38 randomized subjects per group will provide 80% power, to detect a treatment difference over placebo of 3.5 points or greater on the MWT at a 2-sided Type I error level of 0.05, assuming a dropout rate of 10%.

Because of the unknown prognostic importance of a history of cataplexy with EDS on study outcome, a stratification factor will be included based upon that clinical presentation. Stratification would be applied across the entire study, and not within an individual center, and will be reflected in the analytic model. The purpose of the a priori defined subgroup is for hypothesis generation.

Based on the unblinded interim analysis results sample size was re-calculated to maximum of 171 subjects (57 to each treatment group) on mean MWT as primary efficacy endpoint.

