#### 8.4. Secondary Efficacy Endpoint(s) and Analyses (Secondary Estimands)

The secondary efficacy endpoints for this study are:

- Change from baseline in the mean CGI-S score related to EDS at Day 14
- Change from baseline in the mean MWT score at Day 14

The two secondary estimands investigate the efficacy endpoints 'Difference to placebo in the change from baseline in the CGI-S score related to EDS at Day 14' on the ITT population using a MMRM analysis, and the 'Difference to placebo in the Change from baseline in the MWT score at Day 14' on the ITT population using a MMRM analysis. MMRM considers all observed post-baseline assessments of both post-baseline visits (Day 7 and Day 14), , in case of death, the visits after the death will be filled with the worst observed value post-baseline from all subjects, prior to entering the MMRM In the MMRM all missing values will be imputed via direct likelihood based on the assumption of missing at random.

The approaches to handle intercurrent events for secondary endpoints will be consistent with those for the primary endpoint.

The testing of secondary endpoints will be controlled using hierarchical testing methods. The testing of the first secondary efficacy endpoint will be performed in a confirmatory way only, if for the primary efficacy of pooled treatment is significant versus placebo. The confirmatory testing approach will proceed to the second secondary efficacy endpoint only, if pooled active treatment comparison versus placebo is significant for the first secondary efficacy endpoint. Otherwise the results will be considered as exploratory only.

The secondary endpoints will be analyzed similar to the primary efficacy endpoint: using MMRM with multiple imputation and an ANCOVA of Day 7 and Day 14 data with multiple imputation as sensitivity analyses, and by repeating the analyses on PP as supportive analyses.

The time course (Baseline, Day 7, Day 14) of mean values of CGI-S and MWT, respectively, together with +/- standard error of mean will be presented in figures for the ITT and PP populations.

Summary tables by visit by treatment with actual and changes from baseline (if applicable) will be provided for the ITT and PP population.

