**Confidence interval and point estimate:**

A 100(1- $\alpha$ )% Confidence Interval;

$$\frac{W_1 \widehat{\delta}_1 + \sqrt{1 - W_1} \sqrt{W^* - W_1} \widehat{\delta}_2 \pm K^{-1} z_{\alpha/2}}{W_1 + \sqrt{1 - W_1} \sqrt{W^* - W_1}}$$

Point Estimate,  $\widehat{\delta}$  ;

$$\widehat{\delta} = \frac{W_1 \widehat{\delta}_1 + \sqrt{1 - W_1} \sqrt{W^* - W_1} \widehat{\delta}_2}{W_1 + \sqrt{1 - W_1} \sqrt{W^* - W_1}}$$

Where  $W_1$  is time measured on information scale and will be around 50%,  $W^*$  is time measured after doing possible adjustment to initial maximum information ( $W^* > W_1$ ). Please note, Time is measured on the information scale and is rescaled so that the study as originally planned will have maximum information equal to one.  $K^{-1} = S^* \sqrt{((1/n_1) + (1/n_2))}$ , is constant and depends on initial maximum information, where  $S$  is square root of pooled variance.

Deriving a point estimate and confidence interval will be aligned with the CHW test statistic (Lawrence & Hung, 2003). These point estimates will be used for MWT and ESS.

[figure not shown]

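### SAP 11.2 lists only ESS and MWT for the weighted (CHW) analysis, so on the visible text CGI-S, the first confirmatory secondary, has no test with a guaranteed level after the unblinded sample size increase

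*SAP*

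**What the plan says.** **Order of testing.** SAP 8.4 lists two secondary endpoints. The first is "Change from baseline in the mean CGI-S score related to EDS at Day 14" and the second is MWT. CGI-S is confirmatory only if the pooled-dose ESS comparison is significant, and then: "The confirmatory testing approach will proceed to the second secondary efficacy endpoint only, if pooled active treatment comparison versus placebo is significant" for CGI-S. Protocol 14.3.2 gives the same order and its purpose: "To control the Type I error rate, the testing of secondary endpoints will be controlled using hierarchical testing methods".

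**The increase.** SAP 3.6 reports that, on the unblinded interim results, the "sample size was re-calculated to maximum of 171 subjects (57 to each treatment group) on mean MWT as primary efficacy endpoint".

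**The adjusted analysis.** Protocol 14.6 names no endpoint: "In case of sample size increase the weighted Cui, Hung, Wang test-statistic will be used for the combination of the data" from before and after the interim. SAP 11.2 does name endpoints. It describes the CHW "weighted test statistic to analyze the primary and secondary efficacy endpoint (i.e., for total ESS and mean MWT) at the end of the study", and closes the part on estimates and confidence intervals with "These point estimates will be used for MWT and ESS". CGI-S appears in neither sentence.

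**Precedence.** Protocol 14 states: "The SAP will serve as a complement to the protocol and supersedes it in case of differences".

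**Analysis of CGI-S.** SAP 8.4 describes MMRM, with multiple imputation and ANCOVA as sensitivity analyses. It does not mention CHW.

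**The concern.** When the final sample size depends on unblinded stage 1 data, the ordinary test weights the two stages by their realised sizes, and those sizes were themselves chosen from the data. Fixed CHW weights remove that dependence. The exposure is not confined to the endpoint that drove the decision. Any endpoint measured in the same patients and correlated with it is affected. The plan already accepts this, because it applies CHW to ESS, which did not drive the increase. CGI-S is in the same position, and the visible text gives no reason to treat it differently.

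What is at stake is the CGI-S claim itself, in the case where ESS works and CGI-S does not. The false-positive rate for MWT is not raised, because MWT keeps its own CHW test. The plan says the secondary tests are controlled, yet the visible text does not tie the CGI-S step to the statistic that has a guaranteed level.

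**Working it through.** **Plan's own figure.** With a difference of 3.5, SD 5.0, two-sided 0.05 and 80% power, n = 2 × (1.960 + 0.842)² × 25 / 12.25 = 32.04, so 33 per arm, and 33 / 0.9 = 36.7, so 37. The t-test version needs 33.02, so 34, and 34 / 0.9 = 37.8, so 38. The stated 38 per group (114 in all) reproduces. The maximum is 114 + 57 = 171.

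**Inputs from the documents.** Two-sided 5%, which is 2.5% one-sided (z = 1.960). W1 about 50% (SAP 11.2). Final size 114 or 171. Conditional power as in SAP 11.3.

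**Assumptions.** The interim is at 57 of 114. CGI-S has no true effect. The stage 1 correlation ρ between the MWT and CGI-S test statistics is 0.3 to 0.5. The documents give no correlation, and the re-estimation rule is not visible.

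**Weights at the final analysis.**
- The ordinary test gives stage 1 a share t = 57/114 = 1/2 without an increase and t = 57/171 = 1/3 with one.
- CHW keeps 1/2 and 1/2 in both cases.

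**Error of the ordinary CGI-S test.** Let m be the standardised stage 1 deviation of MWT from its true mean. The chance of a false CGI-S success given m is

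e(m, t) = 1 − Φ[(1.960 − √t · ρ · m) / √(1 − t · ρ²)].

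Example with ρ = 0.5 and m = 2:
- t = 1/2: (1.960 − 0.707) / 0.935 = 1.339, so e = 9.0%.
- t = 1/3: (1.960 − 0.577) / 0.957 = 1.444, so e = 7.4%.

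The choice of sample size therefore moves the conditional error. Taking the larger (or smaller) of e(m, 1/2) and e(m, 1/3) at every m and averaging over the normal density bounds every rule driven by MWT:

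| ρ | lowest one-sided error | highest one-sided error |
|---|---|---|
| 0.3 | 2.41% | 2.59% |
| 0.4 | 2.38% | 2.63% |
| 0.5 | 2.34% | 2.66% |
| 1.0 | 2.11% | 2.89% |

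The last row would need CGI-S itself to drive an adversarial rule, so it does not describe this trial.

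**Plausible rules.** I took conditional-power zones with a lower limit of 0 to 50% in steps of 10, an upper limit of 80% or 90%, a mean MWT stage 1 Z of 0, 1, 1.4 or 2, and ρ of 0.3 or 0.5. The one-sided error runs from 2.40% to 2.66%. With a lower limit of 10% or more it runs from 2.40% to 2.61%. Five further rules, checked two-sided at the same correlations, give 4.89% to 5.10%. CHW gives 5.00% whatever the rule.

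**How often the choice of test matters at 171.** The correlation between the two statistics is √(1/2 × 1/3) + √(1/2 × 2/3) = √(1/6) + √(1/3) = 0.986. At 80% power the ordinary statistic has mean 1.960 + 0.842 = 2.802. The CHW mean is 0.986 × 2.802 = 2.761, so CHW power is Φ(2.761 − 1.960) = 78.9%. From the bivariate normal:

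| Power of ordinary test | ordinary only significant | CHW only significant | disagree |
|---|---|---|---|
| 80% | 2.6% | 1.4% | 4.0% |
| 50% | 3.3% | 2.2% | 5.5% |

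**The case against.** **The list may be incomplete, not restrictive.** Section 8 of the SAP, where visible, does not mention CHW for ESS or MWT either, so its silence on CGI-S proves nothing. Protocol 14.6 exempts no endpoint. Both documents say the secondaries are analysed like the primary, and the primary is tested by CHW. An incomplete list need not count as a difference that triggers the precedence clause. This reading is possible. But two separate sentences in 11.2 name the same two endpoints, and the first is worded as a definition. If the broader reading is meant, 11.2 is wrong as it stands, and the same edit corrects it.

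**Redaction.** SAP 11.1, 11.4, 12, 16 and the appendix are blacked out, and the bodies of 8.2 and 8.3 are not visible. Any of them could cover CGI-S. This stands, and it limits the point to the visible text. The two sentences in 11.2 are legible and would still need aligning.

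**Size.** The error moves by at most 0.16 percentage points either way at correlations up to 0.5, and the ordinary test may even be conservative. The correlation and the rules are assumed. The disagreement rate is not an error rate, and no visible text plans two competing CGI-S p-values. All of this stands. It is why the point is minor, and why its weight rests on fixing the choice in advance.

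**Conclusion.** The point holds on the visible text. Read as written, SAP 11.2 leaves out the first confirmatory secondary, and with the precedence clause it narrows a protocol rule that had no such limit. CGI-S is then judged by a test without a guaranteed 5% level, although it gates MWT and shares its stage 1 patients with the data behind the increase.

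The numerical consequence is small and its sign is unknown: 2.34% to 2.66% one-sided against 2.5%. That range assumes an interim at 57 of 114, a final size of 114 or 171, and a correlation of 0.3 to 0.5. The ESS result and the level of the MWT test are untouched. The practical gap is that the text does not clearly fix which CGI-S p-value decides the claim and opens the MWT step. This is worth correcting, but it does not threaten the trial's primary conclusion. Confidence is medium because of the redactions.

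**What to change.** In SAP 11.2:
- Extend the bracketed endpoint list for the CHW test to total ESS, CGI-S and mean MWT.
- Extend the closing sentence on point estimates to the same three endpoints.
- State that all three use the same pre-fixed W1.

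In SAP 8.4, add one sentence: *The p-value used at each step of the hierarchy is the CHW p-value.*

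If redacted text already says this, align 11.2 with it. The change should be made before the final data are unblinded.

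The cost is two phrases, a short statement on W1, one sentence, and one more run of an existing program. CGI-S power falls by about 1 percentage point (80.0% to 78.9% at 171 patients).

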## 8. Efficacy Evaluation

The primary testing approach for efficacy is the statistical comparison of the pooled active SUVN-G3031 dose groups (2 mg/day and 4 mg/day) versus placebo. Additionally, each active dose will be tested against placebo. All statistical tests will be performed at alpha=5% for the two-sided test.

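### The CHW test in SAP 11.2 holds the 5% level only approximately: with a normal reference and estimated standard errors, the two-sided level is about 5.3% to 5.4%

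*SAP*

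**What the plan says.** SAP section 8 makes the primary test "the statistical comparison of the pooled active SUVN-G3031 dose groups (2 mg/day and 4 mg/day) versus placebo" and sets the level: "All statistical tests will be performed at alpha=5% for the two-sided test". Protocol 14.6 uses the CHW statistic if the sample size is increased, and SAP 3.6 reports that after the interim analysis the size was re-calculated to a maximum of 171.

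SAP 11.2 applies the statistic to ESS and MWT and states that "it preserves the type 1 error in case of updated sample size". It forms the statistic "by weighting the stage wise Wald test statistics", each being the estimated difference divided by its standard error, with weights √W1 and √(1 − W1). The matching interval uses the normal quantile z at α/2 together with the square root of a pooled sample variance. The visible text gives no degrees of freedom, t reference or p-value transformation, and no critical value for Z itself. W1 "is time measured on information scale and will be around 50" percent, on a scale where the originally planned study has information 1.

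**The concern.** The CHW argument needs stage statistics that are standard normal and independent under the null hypothesis, with weights fixed independently of the outcome. A Wald ratio with an estimated standard error follows a t distribution, whose tails are heavier. Splitting the trial into two stages means that each standard error is estimated from only part of the data. Judging the weighted sum against 1.96 therefore rejects slightly too often.

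This is the trial's one confirmatory test, and it also opens the hierarchy for the two secondary endpoints (SAP 8.4). The sentence in 11.2 carries no qualification, so a reader would take the 5% as exact.

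**Working it through.** **Inputs**
- Level: two-sided 0.05 (SAP 8).
- Stage 1: about half of 114 = 57 patients (SAP 3.4); at 1:1:1 this is 38 pooled active and 19 placebo.
- Stage 2 with the reported increase: 171 − 57 = 114 patients, 76 and 38.
- W1 = 0.5 (SAP 11.2, approximate).
- SD 5.0 (SAP 3.6), used only for power. The level does not depend on it.
- Assumptions: normal outcomes, equal variances, independent stages, exactly 57 patients in stage 1.

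**The plan's own figures first.** SAP 3.6 states: "Using an SD of 5.0, N = 38 randomized subjects per group will provide 80% power". The target there is an MWT effect of 3.5, with one patient in ten expected to drop out. The normal formula gives 2 × (1.960 + 0.842)² × 5² / 3.5² = 32.04, so 33 per arm, or 37 after dropout. The t-test version gives 33.02, so 34, and 34 / 0.9 = 37.8, so 38. The 38 reproduces. The 5% claim also reproduces under its own premise: with exactly normal stage statistics and any fixed W1, the level is 0.0500.

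**Level with estimated standard errors.** With a pooled SE the degrees of freedom are 57 − 2 = 55 and 114 − 2 = 112. The level is

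P( |√W1 · T1 + √(1 − W1) · T2| > 1.96 ), with T1 ~ t(55) and T2 ~ t(112) independent.

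Numerical integration gives:

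| Case | df, stage 1 / stage 2 | Level at W1 = 0.5 |
|---|---|---|
| Reported increase, pooled SE | 55 / 112 | 5.35% |
| Same, 10% fewer evaluable (51 + 103) | 49 / 101 | 5.40% |
| No increase, pooled SE | 55 / 55 | 5.47% |
| Same, 10% fewer evaluable (51 + 51) | 49 / 49 | 5.53% |
| Reported increase, unpooled SE (Welch) | 36 / 74 | 5.54% |

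Hand check of the first row: a t variable has variance df/(df − 2), so the weighted sum has variance 0.5 × (55/53 + 112/110) = 1.028. Then 1.96/√1.028 = 1.933, and the two-sided normal tail beyond 1.933 is 5.3%.

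Letting the stage 2 size depend on conditional power, under several assumed zones, gives 5.35% to 5.47% by simulation.

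**Does W1 matter?** For the reported increase with a pooled SE, the level is 5.33% at a fixed W1 of 0.40, 5.35% at 0.50 and 5.38% at 0.60. A fixed W1 adds essentially nothing.

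**After the change.** Replace each T by Φ⁻¹(F(T)), where F is the t distribution function with that stage's df. The simulated level is 5.0%.

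**Power cost.** At a 2-point difference with SD 5, the noncentralities are 2/(5 × √(1/38 + 1/19)) = 1.42 and 2/(5 × √(1/76 + 1/38)) = 2.01. Simulated power is 68.4% for the Wald version and 67.4% for the inverse-normal version. Part of that gap is simply the excess level being given up.

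**The case against.** The strongest reply is that this is ordinary large-sample approximation error. A single t statistic with 112 df judged against 1.96 already has level 5.25%, and with 169 df 5.16%. Preserving the level is the recognised property of the CHW weighting under a sample-size change, and the weighting itself is sound. All of that stands, and it is why the point is minor. It does not make the unqualified sentence exact, and the two-stage split enlarges the error somewhat, to 5.35%.

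It is also fair that the SAP prints no reference distribution for Z. The normal reference is inferred from the interval formula. Text around 11.2 and 11.3 and the appendix are redacted and may say more.

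Two stronger readings are tempting and are not supported:

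- **A reader might infer that a W1 of around 50 percent leaves the weight open and pushes the level towards 6%.** Picking W1 after the results to maximise |Z| over an assumed range of 0.45 to 0.55 would give 5.8% with the increase. With Z1 = 2.2 and Z2 = 0.55, p is 0.052 at W1 = 0.50 and 0.045 at 0.55. But nothing in the documents permits such a choice. SAP 11.2 ties W1 to the interim share of the originally planned information, and the range is not a document figure. The absence of an exact value is missing detail, not inflation.
- **A reader might add the single-dose comparisons, at about 5.5%.** SAP 8.1 and 8.4 make only the pooled comparison confirmatory, and SAP 4.3 and 8.5 list the dose-wise analyses as exploratory.

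**Conclusion.** The point holds in a narrow form. If Z is referred to the normal distribution, the confirmatory pooled comparison with 57 + 114 patients has a two-sided level of about 5.3% to 5.4% rather than 5.0%. It is about 5.5% with an unpooled standard error, or had the size not been increased. The excess is therefore roughly 0.3 to 0.5 percentage points.

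This rests on normal outcomes with equal variances, 57 patients in stage 1, independent stages, and a normal reference inferred from the interval. It does not show a fault in the CHW weighting or in the sample-size increase. Severity: minor.

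**What to change.** In SAP 11.2, define Z1 and Z2 as the inverse normal of the one-sided t-based p-value of each stage's Day 14 pooled-versus-placebo contrast, both in the same direction, and name the reference distribution for Z. This restores 5.0%.

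As a clarification, and only if the redacted text does not already do it, print W1 as the single value given by the interim information over the originally planned information. In patient counts that is 57/114 = 0.5 if 57 patients were in the interim analysis.

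The cost is about two sentences in the SAP, no new data, and about 1 percentage point of power at a 2-point difference with SD 5.
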